	
after the Screening Visit. The subject will be scheduled for the Day 1/Baseline Visit.
 
Visit 2 (Day 1/Baseline Visit): At Visit 2 (Day 1/Baseline Visit), subjects with a normal response to CST (post-stimulation serum cortisol > 18 µg/dL) and who continue to meet all the other I/E criteria will be enrolled in the study while subjects with significant abnormal screening results (particularly CST results; post-stimulation serum cortisol ≤ 18 µg/dL) will be discontinued as screen failures. Review clinical laboratory tests (chemistry, hematology, and urinalysis); repeat any lab findings that are abnormal and deemed clinically significant by the investigator per protocol to confirm the findings. Study staff will reconfirm medical history and will record any changes in concomitant medications. All female subjects must have a negative UPT to continue in the study. A limited physical examination including vital signs and weight will be performed and photographs (optional) will be taken. IGA score will be recorded. Study staff will document percent BSA affected with disease in the Treatment Area and the percent BSA to be treated with the test article during the study. Baseline local skin reactions (LSRs) will be recorded prior to test article application. The weight of the canisters will be measured prior to dispensing and test article accountability will be documented. All eligible subjects will apply the first dose in the clinic and be instructed to apply the assigned test article twice daily (approximately every 12 hours) to the psoriatic plaques designated by the investigator until Day 15. Each subject will be given a Subject Instruction Sheet and the study personnel will demonstrate how and where to dispense and apply test article to all the psoriatic plaques within the Treatment Area. The total dose of test article applied per week should be a maximum of approximately 50 grams/week. Any AEs or LSRs (i.e., burning/stinging only) post-application will be recorded. A Subject Diary will also be given to each subject with completion instructions. The subject will be scheduled for the Day 8 visit. Prior to the Day 8 visit, subjects will be requested to i) apply the test article at bedtime on Day 7 and record the time, then ii) withhold application of the test article on the morning of the visit (Day 8).
 
Visit 3 (Day 8 ± 1): If the subject's psoriatic lesions within the Treatment Area are not completely clear, then the subject will complete these Visit 3 (Day 8 ± 1) procedures. However, if the subject's psoriatic lesions within the Treatment Area are completely clear per the Investigator's assessment (i.e., IGA=0), then the subject will complete the Visit 4/EOS procedures; if the CST cannot be performed on Day 8, then the subject will complete Visit 3 procedures, continue dosing of test article, and return on Day 9 (see Optional Visit) to complete the EOS procedures. Subjects who are clear at Day 8, complete CST on Day 8 (or Day 9), and have all EOS procedures completed on Day 8 (or Day 9) will exit the study at Day 8 (or Day 9) following a normal CST result.
 
Subjects will return to the clinic on Day 8 for the study staff to record IGA score, percent BSA affected with disease in the Treatment Area, percent BSA to be treated, review test article compliance (i.e., Subject Diary will be collected, reviewed, and dispensed, as necessary), and collect information on concomitant medications, AEs, and LSRs. Test article accountability will be documented.

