--	--

	
Subjects will have blood drawn on the morning of Day 8 to assess drug concentrations in plasma (trough values - ~12 hours after previous dose). Subjects will apply their morning dose at the clinic after the Day 8 trough blood sample is drawn and continue twice daily (approximately every 12 hours) application of the test article until the next clinic visit. Any AEs or LSRs (i.e., burning/stinging only) post-application will be recorded. The subject will be scheduled for the next visit.
 
Day 9 (Optional Visit - for Subjects that are clear at Visit 3, Day 8): On the following day (Day 9), subjects cleared by Day 8 who could not have a CST performed on Day 8 will have a UPT (females only) and have a CST performed within <math>\pm</math> 1 hour of Screening CST and should, to the extent possible, be initiated between 7 and 9AM. Photographs (optional) will be taken. Any AEs and LSRs will be recorded, any concomitant medications will be documented, all test article and subject diaries will be collected, and the subject will exit the study following a normal CST result.
 
Visit 4 (Day 15 <math>\pm</math> 2 or EOS): Subjects will return to the clinic for the study staff to collect information on AEs, LSRs, concomitant medications, take blood and urine samples for clinical laboratory tests (chemistry, hematology, and urinalysis), draw a final trough PK blood sample prior (~12 hours following previous dose) to EOS CST, and perform the EOS CST. The EOS visit should be scheduled for the morning so that the EOS CST will occur at the same time (<math>\pm</math> one hour) as the CST performed at Visit 1 (Screening) and should, to the extent possible, be initiated between 7 and 9AM. If any of these subjects have adrenal suppression (defined as post-CST cortisol level <math>\leq</math> 18 <math>\mu</math>g/dL), they will be scheduled for one or more post-treatment follow-up visits. Study staff will document IGA score, and percent BSA affected with disease in the Treatment Area and photographs (optional) will be taken. All female subjects will have a UPT. All test article and subject diaries will be collected. The subject will exit the study following a normal CST result.
 
Post-Treatment Follow-up Visits (Suppressed Subjects Only): Any subject who has evidence of adrenal suppression at EOS will return approximately every four weeks BUT no sooner than four weeks (28 days) after the EOS visit, and subsequently approximately every four weeks BUT no earlier than every four weeks (>28 days) thereafter for CST until the adrenal response returns to normal. Follow-up CST will be performed within <math>\pm</math> 1 hour of Screening CST and should, to the extent possible, be initiated between 7 to 9AM. It is important subjects remain off of all forms of steroid therapy (systemic, topical, injectable, etc.) during this post-treatment assessment period. See Section 9.3 for procedures to be performed at these post-treatment follow-up visits.

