	
the overall or “average” degree of severity taking into account all of the subject’s psoriatic lesions in the Treatment Area (excluding those on the face, scalp, groin, axillae and other intertriginous areas) by the investigator or designee. This evaluation takes into consideration the three individual characteristics of psoriasis (plaque elevation, scaling, and erythema) with the IGA score at each visit representing the average of plaque elevation, scaling, or erythema that is present amongst all of the lesions eligible for treatment.
 
Percent Body Surface Area Affected with Disease: The percent BSA affected with psoriasis in the Treatment Area (excluding the face, scalp, groin, axillae, and other intertriginous areas) will be estimated at the Screening Visit, Baseline Visit/Day 1, Day 8, and Day 15.
 
Percent Body Surface Area Treated with Test Article: The percent BSA treated with the test article will be estimated at Baseline Visit/Day 1 and Day 8 (for subjects who have not cleared).
 
Test Article Compliance: Subjects will apply the first dose of test article to all plaques within the Treatment Area under staff supervision. At each visit, subject diaries will be reviewed to determine test article doses taken since the last visit and subjects will be counseled regarding compliance if necessary. Subjects will be instructed to record the date that the last dose was applied. All dispensed canisters of test article will be weighed at each visit.
 
Local Skin Reactions: At each visit, subjects will be evaluated for the presence of any LSRs associated with the topical application of corticosteroids including telangiectasia, skin atrophy, burning/stinging, and folliculitis. Burning/stinging will be evaluated post-application at Baseline Visit/Day 1 and Day 8 (for subject who have not cleared).
 
Adverse Events: All AEs will be recorded. At each visit after the Baseline Visit/Day 1, subjects will also be questioned specifically about the status of any ongoing AEs.
 
Clinical Laboratory Tests Urine and blood samples will be collected from each subject for safety laboratory analysis at Visit 1/Screening, Visit 2/Baseline (if applicable), and Visit 4/EOS. Any new or worsening clinically significant abnormalities at Visit 4/EOS will be recorded as AEs.
 
Cosyntropin Stimulation Test: The EOS visit (i.e., the end of the assigned treatment period) should be scheduled in the morning so that the CST will occur at the same time (<math>\pm</math> one hour) as the CST performed at Visit 1 (Screening). The Screening CST will be initiated between 7 and 9AM; all follow-up CSTs should, to the extent possible, be initiated between 7 and 9AM.

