--	--

	
Pharmacokinetic Assessment:
 
Eligible subjects will have blood drawn at Screening for baseline drug concentration in plasma. On Day 8, all subjects, regardless of lesion clearance, will have blood drawn for assessment of trough drug concentration in plasma. At the Day 15 visit, subjects who have continued to treat lesions will have a final assessment of trough drug concentration in plasma approximately 12 hours (<math>\pm</math> 30 minutes) after their Day 14 evening application and just prior to the initiation of the CST.

Study Endpoints	
HPA Axis Response to Cosyntropin - Measurement of serum cortisol concentrations after stimulation of the adrenal cortex with cosyntropin (Cortrosyn® tests). HPA axis suppression is defined as a post-stimulation serum cortisol level <math>\leq</math> 18 <math>\mu</math>g/dL assessed at the end of study.
 
Plasma Levels of HBP - Trough HBP concentrations in plasma will be assessed at Screening, Day 8, and Day 15 approximately 12 hours (<math>\pm</math> 30 minutes) post-treatment.
 
Other Safety Endpoints - AEs, LSRs, clinical laboratory tests, UPTs, dosing compliance, and extent of exposure.

Sample Size Calculations	No formal power calculations were performed to establish the sample size. The number of subjects enrolled who complete the study is historically consistent with other HPA/PK studies.

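### The dose before Visit 3 is tied to bedtime rather than to the 12-hour trough, so a late bedtime and a 7–9 AM visit give an early Day 8 sample

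*Combined protocol and SAP*

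**What the plan says.** All references are to the Protocol Synopsis.

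- **Dose before Visit 3** (Study Procedures, Visit 2): subjects are to "apply the test article at bedtime on Day 7 and record the time" and to omit the Day 8 morning dose at home. The bedtime dose therefore starts the trough interval.
- **Day 8 draw** (Study Procedures, Visit 3): "Subjects will have blood drawn on the morning of Day 8 to assess drug concentrations in plasma", described as a trough about 12 h after the previous dose.
- **Endpoint** (Study Endpoints, Plasma Levels of HBP): "Trough HBP concentrations in plasma will be assessed at Screening, Day 8, and Day 15 approximately 12 hours", with a tolerance of ± 30 minutes.
- **Subjects clear at Visit 3** (IGA = 0): they complete the end-of-study procedures that day, including the CST. The alternative reads "if the CST cannot be performed on Day 8, then the subject will complete Visit 3 procedures, continue dosing of test article", with a return on Day 9.
- **CST timing** (Visit 4, and Study Measurements, Cosyntropin Stimulation Test): within one hour of the Screening CST time, and "all follow-up CSTs should, to the extent possible, be initiated between 7 and 9AM". At the end-of-study visit the trough is drawn before the CST.
- **Day 15 comparison** (Study Measurements, Pharmacokinetic Assessment): the final trough is timed "after their Day 14 evening application and just prior to the initiation of the CST". It is linked to an evening dose, not to bedtime.

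**The concern.** The visit is booked before the dose time is known, and clearance is judged only at the visit. A site that wants to keep the same-day CST available must book Visit 3 early for anyone who might clear. A subject with a late bedtime can then follow the dosing instruction exactly and still be sampled well short of 12 h.

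Trough concentration is the only pharmacokinetic endpoint, summarized descriptively in a study of about 25 enrolled subjects. Mixing samples taken at 8–11 h with samples at 12 h blurs what the Day 8 summary represents. If mistimed draws were instead ruled significant deviations, those subjects would leave the PK population. For a subject who exits early, Day 8 is the only on-treatment sample: the Day 15 sample is for "subjects who have continued to treat lesions will have a final assessment of trough drug concentration in plasma", and the Day 9 visit lists no PK draw.

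**Working it through.** **Inputs from the synopsis:** trough window 11.5–12.5 h after the dose; Screening CST at 7–9 AM; end-of-study CST within ± 1 h of the Screening CST and at 7–9 AM where feasible; maximum about 50 g/week; two applications a day.

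**Assumption:** bedtime between 20:00 and 23:00. The documents give none.

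**1. Dose times that give an in-window trough at 7–9 AM.** Dose time = draw time − 12.5 h to draw time − 11.5 h.

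- Earliest dose: 07:00 − 12.5 h = 18:30.
- Latest dose: 09:00 − 11.5 h = 21:30.

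**2. Hours since dose, by bedtime.** Interval = draw time − bedtime. In-window draw = bedtime + 11.5 h to bedtime + 12.5 h.

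| Bedtime | Draw 07:00 | Draw 08:00 | Draw 09:00 | In-window draw |
|---|---|---|---|---|
| 20:00 | 11 h | 12 h | 13 h | 07:30–08:30 |
| 21:00 | 10 h | 11 h | 12 h | 08:30–09:30 |
| 22:00 | 9 h | 10 h | 11 h | 09:30–10:30 |
| 23:00 | 8 h | 9 h | 10 h | 10:30–11:30 |

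For bedtimes of 22:00 and 23:00, no draw from 7 to 9 AM is in window.

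**3. Latest dose that allows both an on-time trough and a same-day CST.** With the trough drawn just before the CST, latest dose = (Screening CST + 1 h) − 11.5 h.

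| Screening CST | Latest same-day CST | Latest dose |
|---|---|---|
| 07:00 | 08:00 | 20:30 |
| 08:00 | 09:00 | 21:30 |
| 09:00 | 10:00 (± 1 h rule alone) | 22:30 |
| 09:00 | 09:00 (7–9 AM also kept) | 21:30 |

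In reverse, the earliest compatible Screening CST = bedtime + 11.5 h − 1 h. A 21:00 bedtime gives 07:30; 22:00 gives 08:30; 22:30 gives 09:00. A 23:00 bedtime gives 09:30, which is outside the Screening window, so the two cannot be combined.

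**4. Extra exposure on the Day 9 route.** This route adds the Day 8 morning and evening applications. At the weekly maximum, 50 g ÷ 14 applications = 3.57 g each, and 2 × 3.57 = 7.1 g.

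**The case against.** The strongest reply is that every window can be met as the plan stands. Visit 3 is not itself fixed to 7–9 AM. The site is told to draw in the morning at about 12 h, and a 22:00 or 23:00 dose still gives an on-time draw before noon. A subject who is not clear has no CST that day, so no conflict arises. A cleared subject has the Day 9 route, and since the Day 8 PK sample is required of everyone, that route loses no sample. Exclusion criterion 16 removes irregular sleepers, so bedtime is largely predictable when the visit is booked, and the recorded dose time makes an early sample detectable. Few subjects may clear in one week from an entry IGA of at least 3; the documents give no rate. The Subject Instruction Sheet, which is not available here, may be more specific.

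Most of this is correct, and it limits the point to a minor one. It does not remove it. Waiting for 12 h can forfeit the first-choice CST day and prolong dosing of cleared skin. Criterion 16 concerns regularity, not the hour: a regular 22:30 bedtime is eligible. The general twice-daily instruction gives an interval of roughly 12 h, but the specific pre-visit instruction says bedtime. Recording the time allows detection, not prevention, and the stated PK analysis does not mention elapsed time.

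**Conclusion.** The concern holds, as a minor design point. Any dose after 21:30 puts every 7–9 AM draw below the 11.5 h limit; at assumed bedtimes of 22:00–23:00 the sample is 1 to 4 h short of 12 h. The alternatives are a later draw, which may give up the same-day CST for a cleared subject, and the Day 9 route, at up to about 7 g of extra product.

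The conclusion depends on some subjects having late bedtimes and on sites booking Visit 3 early to keep the CST available. The number affected cannot be estimated, because neither bedtimes nor the one-week clearance rate is given. The effect on measured concentration is also unknown, because no half-life or concentration–time profile is given. The Day 15 adrenal assessment is not affected. Only the synopsis could be checked.

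**What to change.** In Study Procedures, Visit 2, replace the bedtime instruction with one to apply the dose on the evening before the visit, 12 h (± 30 min) before the scheduled blood draw, and set the draw time from the subject's Screening CST time. A Screening CST at 07:00, 08:00 or 09:00 then gives a dose at about 19:00, 20:00 or 21:00. Draws at those times fall 11.5–12.5 h after the dose, and the same-day CST stays available. Referring to the evening before the visit also suits the ± 1 day visit window better than a fixed Day 7.

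Use the same instruction before Visit 4; this largely restates the timing already given under Pharmacokinetic Assessment. Optionally, report actual hours since the last application beside the Day 8 and Day 15 troughs.

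The cost is one sentence, repeated for Visit 4, and at most one table column. Subjects must dose at a set time on two evenings. No visits or samples are added.

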	
determined for the total amount of test article used and average amount of test article used per application by each subject.
 
An approximation of the amount of test article applied per cm^2 will be determined based on the average amount of test article used per application and an estimate of the percent BSA treated with the test article at Visit 2/Baseline. The BSA treated with test article (in square centimeters) will be determined from the Mosteller calculation [1].
 
Urine Pregnancy Tests A listing of UPT results will be prepared.
 
Local Skin Reactions The frequency distributions of the severities of LSRs associated with topical application of corticosteroids including telangiectasia, skin atrophy, burning/stinging, and folliculitis will be summarized at Baseline and all follow-up visits.
 
Adverse Events All subjects enrolled in the study who were dispensed and applied test article at least once will be included in the safety analyses (Safety population). All AEs reported during the study will be listed, documenting onset, whether therapy was required, any change in test article dosing, severity, possible relationship to test article, and outcome. Verbatim terms on the electronic case report forms (eCRFs) will be linked to preferred terms (PTs) and system organ class (SOC) using the Medical Dictionary for Regulatory Activities (MedDRA) mapping system. All reported AEs will be summarized by the number of subjects reporting AEs, SOC, PT, severity, and relationship to test article.
 
Clinical Laboratory Tests Clinical laboratory tests will be evaluated for any clinically significant changes during the study period. All laboratory data (hematology, chemistry, and urinalysis) will be listed and reported in the units received by the laboratory. Shift tables by analyte and by out of range flag will be presented to facilitate the evaluation of change from Visit 1/Screening to Visit 4/EOS.
 
HPA Axis Suppression Analysis HPA axis responses to CST will be dichotomized to normal and abnormal. An abnormal HPA axis response (HPA suppression) is defined as a 30-minute post-stimulation serum cortisol level of <math>\leq 18</math> <math>\mu</math>g/dL at the end of study. The proportion of subjects manifesting laboratory evidence of adrenal suppression at the end of study will be summarized. The mean increases in serum cortisol levels after stimulation will also be summarized at the end of study. In addition, descriptive statistics for the daily dose of test article will be tabulated separately for suppressed and non-suppressed subjects. Post-treatment follow up data will be summarized for subjects determined to have laboratory based evidence of adrenal suppression at the end of study or early termination visit.

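### The planned local skin reaction tables do not link a subject's later grades to the pre-dose grade, or count subjects ever affected; one added table would do both

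*Combined protocol and SAP*

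**What the plan says.** All references are to the Protocol Synopsis in the combined protocol and SAP.

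- **Planned analysis.** Statistical Methods, Local Skin Reactions, has one sentence. Its subject is "The frequency distributions of the severities of LSRs associated with topical application of corticosteroids", and it ends "folliculitis will be summarized at Baseline and all follow-up visits".
- **Baseline data.** Study Procedures, Visit 2: "Baseline local skin reactions (LSRs) will be recorded prior to test article application".
- **Later data.** Study Measurements, Local Skin Reactions: "At each visit, subjects will be evaluated for the presence of any LSRs". Burning/stinging is graded again after the clinic application on Day 1, and on Day 8 for subjects not yet clear.
- **Status.** Study Endpoints puts LSRs among the other safety endpoints: "AEs, LSRs, clinical laboratory tests, UPTs, dosing compliance, and extent of exposure".
- **Laboratory data, by contrast.** Statistical Methods, Clinical Laboratory Tests: "Shift tables by analyte and by out of range flag will be presented to facilitate the evaluation of change". Study Measurements adds, for laboratory findings: "Any new or worsening clinically significant abnormalities at Visit 4/EOS will be recorded as AEs".

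The synopsis states no shift table, change-from-Baseline summary, ever-affected count or listing for LSRs. It also has no rule that a new or worsened LSR is recorded as an adverse event.

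**The concern.** The safety question for a topical corticosteroid is which reactions appeared or got worse during treatment. There is no control arm, so the subject's own pre-dose state is the main reference. The plan collects that reference, but the stated summary does not use it subject by subject.

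A severity distribution at each visit is a set of separate margins. Equal counts at Baseline and EOS can mean that the same subjects have the reaction throughout, or that some cases resolved while others began. Nor do counts at two post-Baseline visits show how many different subjects were affected at some time.

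At stake is whether a named safety endpoint yields an incidence of new or worsened reactions from a prespecified table. Otherwise a definition of new or worsened would have to be chosen after the results are seen. With about 25 subjects, each one moves the percentage by 1/25 = 4 points.

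**Working it through.** There is no planned figure to reproduce: the synopsis says that no power calculation was made, and it gives no expected LSR rates. The check is what the planned tables can and cannot identify.

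**Inputs.** n = 25, the approximate enrollment in the synopsis; 20 is the minimum number of evaluable subjects. All reaction counts below are assumed.

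**1. New cases at one follow-up visit.** Let b be the number with the reaction at Baseline, f the number at follow-up, n the number assessed at both, and r the number with it at both. New cases = f − r. The margins limit r to between max(0, b + f − n) and min(b, f). So new cases lie between max(0, f − b) and min(f, n − b).

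| b | f | n | Lower: max(0, f − b) | Upper: min(f, n − b) | New cases |
|---|---|---|---|---|---|
| 4 | 4 | 25 | max(0, 0) = 0 | min(4, 21) = 4 | 0 to 4 (0% to 16%) |
| 3 | 6 | 25 | max(0, 3) = 3 | min(6, 22) = 6 | 3 to 6 (12% to 24%) |
| 5 | 3 | 25 | max(0, −2) = 0 | min(3, 20) = 3 | 0 to 3 (0% to 12%) |
| 0 | 3 | 25 | max(0, 3) = 3 | min(3, 25) = 3 | exactly 3 (12%) |

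With n = 20 the count ranges in all four rows are the same. The margins fix the number of new cases only where nobody or everybody has the reaction at one of the two visits. Otherwise the net rise is a lower bound.

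**2. Subjects ever affected.** Take no cases at Baseline, 2/25 at Day 8 and 2/25 at EOS. The number of different subjects lies between max(2, 2) = 2 and min(25, 2 + 2) = 4, so 2/25 = 8% to 4/25 = 16%. A reaction-free Baseline does not remove this gap.

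**3. Who is in the EOS table.** Subjects clear at Day 8 leave at Day 8 or 9. They complete the EOS procedures first, and those include LSRs, so an EOS grade exists for them. The denominator shrinks only if the last column is built strictly as Day 15 and not as EOS. The synopsis does not say which.

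**4. Are Baseline reactions plausible?** Exclusion criterion 5 bars topical corticosteroids for 14 days before Screening Part B, and also from Part B to the first dose. Baseline should ideally fall at least 20 days after Screening. Counting those 20 days from Part B, the steroid-free interval is about 14 + 20 = 34 days. Earlier use is allowed, so lasting changes are possible. Their frequency is unknown.

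**5. Which grade is Baseline for burning/stinging?** It is graded before and after the first application on Day 1. The planned summary does not say which grade stands in the Baseline column.

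**The case against.** The strongest case against has five parts.

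- **Only the synopsis is available.** It refers to body sections that are not supplied, where further LSR tables or listings could be specified. This stands: the finding is limited to the supplied text.
- **The data exist.** A reader might infer that the trial cannot report how many reactions began or worsened on the foam. The documents do not support that. Grades are taken before dosing and at each visit, and nothing says the per-visit summary excludes other tables.
- **Adverse event reporting may catch new reactions.** Adverse events are listed with onset, severity and relationship, so a reaction judged to be an adverse event would appear there. This helps only in part, because no LSR-to-adverse-event rule is stated. The new-or-worsening rule covers laboratory abnormalities only.
- **Two supporting arguments are easily overstated.** A reader might infer that early exit at Day 8 removes subjects from the EOS assessment, or that a 14-day washout makes Baseline steroid changes likely. Steps 3 and 4 of the working show otherwise: these subjects have an EOS grade, and the steroid-free interval is about 34 days on the ideal schedule.
- **The upper bounds are extremes.** Four new cases from 4/25 and 4/25 needs all four Baseline cases to resolve in two weeks of treatment while four other subjects develop the reaction. If Baseline reactions persist, the net rise equals the number of new cases. That is correct, but the planned tables cannot show whether they persisted.

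Planning shift tables for laboratory data does not oblige the sponsor to use them for LSRs. It does show that the method is already part of the plan.

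**Conclusion.** The point holds as a gap in the planned output. On the supplied synopsis, the stated tables do not link later LSR grades to the subject's own pre-dose grade, and they do not give the number of subjects ever affected. With Baseline cases present they in general bound the number of new cases and do not determine it. With none present, the count at each visit is exact but the total across visits is not.

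The size is small. LSRs are one of six other safety items in a descriptive single-arm study, and no HPA axis or pharmacokinetic conclusion depends on them. The illustrated ranges (0% to 16% new, 8% to 16% ever affected) rest on assumed counts and 25 subjects assessed at each visit; they are not forecasts. The change is a free improvement, not a correction that the trial's main conclusions need.

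**What to change.** In Statistical Methods, Local Skin Reactions, add for each of the four reactions:

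1. A shift table from the Baseline grade, taken before the first application, to the worst grade after it, up to and including EOS.
2. The number and percent of subjects with a new or worsened reaction, meaning a worst later grade above their own Baseline grade, with each subject counted once.
3. A statement that the EOS assessment of subjects who exit at Day 8 or 9 is included.
4. A statement that post-application burning/stinging on Day 1 and Day 8 counts as post-Baseline.

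Keep the per-visit frequencies as support. If the body of the protocol or a fuller SAP already specifies such a table, a cross-reference is enough.

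The cost is one table per reaction and a few sentences of text. It uses data already collected and changes no visit, procedure or sample size.
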